Hypothesis I-a: C-tDCS will be safe in AIS patients receiving EVT with no increased risk of symptomatic intracranial hemorrhage (SICH) within the 24-hour period after EVT. Hypothesis I-b: C-tDCS will not increase the rates of asymptomatic intracranial hemorrhage, early neurological deterioration (NIHSS during the 24-hour period after stimulation), 90-day mortality, and all serious adverse events. Hypothesis I-c: Majority of AIS patients ($\geq 90\%$) will tolerate the C-tDCS by completing at least 75% of the stimulation period with no major stimulation related pain, discomfort and skin changes.

Specific Aim II: To determine the feasibility of delivering C-tDCS as an adjunct and bridge to EVT.

Hypothesis II-a: Adjunctive C-tDCS after endovascular thrombectomy will be started more rapidly after the end of ET procedure over the course of the study and in the last 10 patients, median time from end of ET procedure to C-tDCS initiation will be ≤ 10 minutes. Hypothesis II-b: Bridging C-tDCS prior to endovascular thrombectomy will be started more rapidly over the course of the study and in the last 4 patients, median time from randomization to C-tDCS initiation will be ≤ 10 minutes.

Specific Aim III: To explore the potential imaging and clinical efficacy of tDCS in AIS as an adjunct and bridge to EVT.

1) Early and late penumbral salvage, defined as proportion of penumbral tissue on baseline multimodal MRI that does not proceed to infarct on 2-hour and 24-hour MRI (PWI); 2) Early and late collateral enhancement, evidenced by reduced perfusion lesion volume on 2-hour and 24-hour perfusion-weighted MRI (PWI); 3) Early and late reduction in infarct growth from baseline to 2-hour and 24-hour MRI; 4) Early improvement in neurologic deficit (NIHSS at 24h); 5) Improvement in final 3-month disability and quality of life (modified Rankin scale, AMC Linear Disability Scale, EQ-5D, and Barthel Index)

Impact

This in-hospital safety trial, will identify C-tDCS dose regimens that are feasible, well-tolerated, and preliminarily safe in patients with acute ischemic stroke who undergo ET. Study finding will identify the most promising dose regimens to advance to phase 2b and pivotal phase 3 efficacy trials for three patient populations with pressing need for improved therapies: 1) thrombectomy-eligible patients arriving directly to thrombectomy-capable hospitals who would benefit from post-arrival brain protection; 2) thrombectomy-eligible patients arriving initially

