This proposal is a prospective, single-center, dose-escalation safety, tolerability and feasibility study of C-tDCS as adjunctive and bridging neuroprotection in acute stroke patients undergoing endovascular thrombectomy. Patients with less than a complete EVT reperfusion (the thrombolysis in cerebral infarction (TICI) grading of <2c and 3) will be receiving at least one cycle of adjunct C-tDCS after EVT and at higher dose tiers, one cycle of bridging C-tDCS will be administered before EVT and if EVT results in TICI < 2c/3, then two cycles of adjunct EVT will be applied after EVT. The primary safety endpoints will be symptomatic intracranial hemorrhage during the 24-hour period after thrombectomy. Secondary measures of safety will include asymptomatic intracranial hemorrhage, early neurological deterioration, 3-month mortality and all serious adverse events. Tolerability will be judged based on the percentage of the patients completing the protocol-assigned stimulation treatment and secondarily, the rate and severity of cutaneous, neurologic, nociceptive or

other adverse effects will be assessed. Feasibility endpoints will analyze the speed with which tDCS will be implemented. Finally, we will explore signals of potential efficacy by examining the imaging evidence of infarct growth, and clinical outcomes of early neurologic deficit evolution, and 3-month global disability and health-related quality of life.

D2. Technology

D2.1. tDCS Device and Stimulation Parameters

The study will employ a Soterix™ high-definition DC-Stimulator, owned by the principal investigator. This tDCS unit consists of a stimulator, 4x1 HD interface and an adjustable cap with pre-maid openings that quickly and easily fits different head sizes. (Figure 5). The cap will be loaded with plastic electrode holders. These will be filled with conductance gel (Signa® gel), 1 cm² electrodes will be placed in the holders, and the holder then locked.

D2.2. Montage

The electrode positioning montage will be a 4 to 1-ring configuration, with the center or active electrode connected to cathode and the 4 reference or return electrodes connected to anode. The 4 to 1-ring configuration is chosen to focus the stimulation to the penumbral region. (Fig 6)

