Tier 6 - 2 mA, in 3 treatment cycles. First cycle will be a 20 min cycle, administered after initial imaging either in the Roland Reagan Medical Center or mobile stroke unit and prior to arterial puncture (cycle will be shorter than 20 minutes if EVT puncture is ready to proceed, in order not to delay EVT). The second cycle will start at the conclusion of the EVT procedure in patients with TICI<2c and 3 and negative immediate post-EVT CT scan for a definitive evidence of ICH (and not sooner than 20 minutes after the end of the first cycle), and will last 20 minutes. The third cycle will start 20 minutes after the end of the second cycle, and will last 20 minutes.

Patients in the sham stimulation arm at all the tiers will have the cap and electrodes in place, but without any delivered electrical stimulation. While the highest dose tier in this study is expected to be fully safe, based on preclinical and clinical studies ^{11,18}, since this is a first-in-human study in acute stroke, a formal escalation to higher dose tiers is prudent.

[figure not shown]

Figure 7. This figure shows the 6 escalating tiers. Blue represents 1 mA, purple shows 2 mA of C-tDCS. The black/white neuroangi suite icon represents the endovascular thrombectomy (EVT) procedure, occurring before the adjunctive C-tDCS at all tiers if EVT results in a less than a complete recanalization (TICI <2c, 3). At tiers 5 and 6, bridging C-tDCS occurs for up to 20' before EVT. Symptomatic ICH (SICH) in none of the three C-tDCS patients in a tier will result in escalation. However, if SICH occurs in one C-tDCS patient, 3 more C-tDCS patients and 1 more sham will be enrolled at the same tier.

D.4. Management pre, during, and post adjunctive stimulation period

As soon as the endovascular thrombectomy (EVT) ends, a CT head will be obtained in patients with less than a complete EVT reperfusion (TICI < 2c,3) and if negative for definitive evidence of intracranial hemorrhage, then the patient will be randomized, and the adjunct stimulation will be initiated in neurosurgical intensive care unit according to the tier that patient is assigned to.

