The lead tolerability endpoint is completion of the protocol-assigned stimulation treatment without early cessation due to cutaneous, neurologic, nociceptive or other adverse effects. Experience with tDCS in post-stroke patients indicates only infrequent cutaneous (itching, tingling) adverse effects are likely to occur. Accordingly, for the current study, a patient will be considered to have tolerated the procedure if at least 75% of the stimulus period was completed. The treatment will be considered generally tolerable if, among all enrolled patients, tolerated procedures are achieved in $\geq 90\%$ of patients, assessed with a one-sided p value of 0.025. Secondary tolerability endpoints will be the rate and severity of cutaneous, neurological, and pain items of the technician-filled (Figure 7), descriptively compared between active treatment and sham patients, and between higher and lower dose tiers.

E.3.4. Feasibility Endpoint Analysis (Specific Aim 2)

A time-motion analysis and mock run-throughs will be conducted prior to first enrollment. Nonetheless, it is anticipated that processes to optimize rapid placement of the cap and electrodes will continue to improve with experience gained from initially enrolled patients. The predefined success threshold for feasibility will be median times from randomization to bridging C-tDCS initiation and the time from end of EVT procedure to adjunctive C-tDCS initiation ≤ 10 minutes in the last 4 and 10 enrolled patients, respectively.

E.3.5. Exploratory Efficacy Endpoints Analysis (Specific Aim 3)

E.3.5.1. Exploratory Clinical Efficacy Endpoints

This study is underpowered to definitively determine efficacy, so all clinical efficacy analyses will be purely exploratory and descriptive. Four clinical outcome measures were selected based on their reliability, familiarity to the neurologic community, and adaptability for use in patients who have had a stroke. These endpoints are: the modified Rankin Scale (mRS), a rating of global disability; the Barthel Index (BI), a measure of instrumental activities of daily living; the National Institutes of Health Stroke Scale (NIHSS), a measure of neurologic deficit severity; and the EuroQol (EQ-5D), an assessment of health-related quality of life; and AMC Linear Disability Scale, a granular degree of disability.

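### Section E.3.3's tolerability rule has no stated null, pools sham patients and drops the symptom condition of Hypothesis I-c, so its verdict is not determined and does not match I-c

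*Combined protocol and SAP*

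**What the plan says.** Hypothesis I-c (Section A, Specific Aims) is that at least 90% of patients "will tolerate the C-tDCS by completing at least 75% of the stimulation period with no major stimulation related pain, discomfort and skin changes". It has two patient-level parts: completion, and absence of major effects.

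E.3.3 opens by naming the lead endpoint as completion of assigned stimulation "without early cessation due to cutaneous, neurologic, nociceptive or other adverse effects". Its scoring rule is then that "a patient will be considered to have tolerated the procedure if at least 75% of the stimulus period was completed". The overall rule follows: "The treatment will be considered generally tolerable if, among all enrolled patients", the rate is at least 90%, "assessed with a one-sided p value of 0.025". Symptoms come after that: "Secondary tolerability endpoints will be the rate and severity of cutaneous, neurological, and pain items", compared descriptively by arm and by dose tier.

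D.1 takes the same line as E.3.3: "Tolerability will be judged based on the percentage of the patients completing the protocol-assigned stimulation treatment", with adverse-effect rate and severity second.

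Under D.4 (Dose Tiers and Randomization), sham patients "will have the cap and electrodes in place, but without any delivered electrical stimulation". Randomization is 3:1, and E.2.1 derives a total of 24 to 48 from the 3+3 rule alone. No power or critical count is given for tolerability.

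**The concern.** Three things are unsettled in one decision rule.

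1. **Criterion.** A 90% bar and a one-sided level are given, but not the null, the direction or the test. The same data can then be declared tolerable or not, according to a reading chosen after the results are known.
2. **Population.** One patient in four in the denominator receives no current and cannot inform tolerance of C-tDCS.
3. **Definition.** A patient who completes 75% with a major pain or skin effect counts as a success under E.3.3 and as a failure under I-c.

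At stake is the *generally tolerable* label for part of Specific Aim I. D.6.10.2 lists tolerability among the results to be weighed in deciding on the next stage of development.

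**Working it through.** **Sample size.** Six tiers × (3 active + 1 sham) = 24. If every tier expands, 6 × 2 × 4 = 48. This reproduces E.2.1. Active/sham numbers are 18/6 at N=24 and 36/12 at N=48, moving in steps of 3/1 per expanded tier.

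**1. Criterion.** X is the number tolerating out of N enrolled; all probabilities are exact binomial.

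| Reading | N=24 passes from | N=48 passes from |
|---|---|---|
| Reject rate ≤ 90% | not possible | 48/48 |
| Fail only if significantly below 90% | 18/24 (75%) | 39/48 (81%) |
| Reject rate ≤ 50% (I-c speaks of a majority) | 18/24 (75%) | 32/48 (67%) |
| Observed rate ≥ 90% | 22/24 | 44/48 |

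- Row 1: with no failures p = 0.9^N. 24/24 gives 0.080, 28/28 gives 0.052 and 32/32 gives 0.034, all above 0.025. 36/36 gives 0.0225. At N=48, 48/48 gives 0.0064 but 47/48 gives 0.040.
- Row 2: P(X≤17 | 24, 0.9) = 0.0075 and P(X≤18) = 0.028, so 18 passes. P(X≤38 | 48, 0.9) = 0.019 and P(X≤39) = 0.046, so 39 passes.
- Row 3: P(X≥18 | 24, 0.5) = 0.011 and P(X≥17) = 0.032. P(X≥32 | 48, 0.5) = 0.015 and P(X≥31) = 0.030.
- Row 4: 0.9 × 24 = 21.6, rounded up to 22; 0.9 × 48 = 43.2, rounded up to 44.

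A result of 22/24 therefore fails the first reading and passes the other three. No assumed rate is needed for this part.

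**2. Population.** The documents give no completion rates, so these are illustrative. Take the 90% point threshold and a true active completion rate of 85%. Active-only needs 17/18 or 33/36.

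| Sham completion | N=24: pooled vs active-only | N=48: pooled vs active-only |
|---|---|---|
| 100% | 48% vs 22% | 36% vs 19% |
| 95% | 41% vs 22% | 26% vs 19% |
| 85% (same as active) | 28% vs 22% | 13% vs 19% |

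In the first row the pooled threshold leaves 22 − 6 = 16 of 18 active, or 44 − 12 = 32 of 36: P(X≥16 | 18, 0.85) = 0.480 and P(X≥32 | 36, 0.85) = 0.355. Active-only: P(X≥17 | 18, 0.85) = 0.224 and P(X≥33 | 36, 0.85) = 0.191. So with full sham completion an active rate of 88.9% passes when pooled and fails on its own. With equal completion at N=48, pooling is the stricter rule. If the true active rate is 98% and all sham complete, the difference is small: 99.5% vs 95.0% (N=24) and 99.9% vs 99.4% (N=48).

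**3. Definition.** Active patients only, 90% point threshold, 98% completing (illustrative). The I-c rate is 0.98 × (1 − share of completers with a major effect).

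| Completers with a major effect | I-c rate | Passes, 18 active | Passes, 36 active |
|---|---|---|---|
| 0% (completion alone) | 98.0% | 95% | 99% |
| 1% | 97.0% | 90% | 98% |
| 2% | 96.0% | 84% | 95% |
| 5% | 93.1% | 64% | 77% |
| 10% | 88.2% | 36% | 37% |

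Adding the condition can only lower the rate or leave it unchanged.

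**The case against.** E.3.3 shares the 75% and 90% figures with I-c, and its first sentence ties failure to stopping for adverse effects. A reader might infer that it does not test I-c at all; given these shared elements, that is too strong. D.1 agrees with E.3.3 on completion, so the mismatch could be loose wording in I-c and not an analysis error. That point stands: the documents do not say which text governs, and the request is to reconcile them. It does not remove the gap, because stopping early and having a major effect while completing are different events.

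A reader might also infer that pooling makes the treatment look better tolerated. The documents give no completion rates, and with equal completion in both arms pooling lowers the chance of passing at N=48. Only the mismatch of population is established, not a direction.

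E.3.3 expects only infrequent cutaneous effects such as itching and tingling. If major effects occur in 1% of completers, the omitted condition changes little (90% against 95% with 18 active). That also stands.

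Finally, the label gates nothing. Under E.2.3.1 escalation rests on SICH and the DSMB's review of safety data, and symptom severity is still shown by arm and tier. This limits the consequence, but does not make the criterion usable.

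**Conclusion.** The point holds on all three counts, with unequal weight. The missing null is the firmest: without any assumed rate, the pass mark at N=24 runs from 18/24 to unattainable, and at N=48 from 32/48 to 48/48. The pooling of sham and the absent symptom condition are plain from the text. Their size is not known, because every completion and symptom rate used above is an assumption; the effect ranges from negligible to enough to reverse the verdict.

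It would go too far to conclude that an intolerable regimen could escalate because of this rule, or that major symptoms would go unreported. Neither follows from the documents. What is affected is the binary label and what it can be taken to mean. This should be fixed before analysis.

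**What to change.** In E.3.3:

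- **Population.** Base the lead tolerability rate on active patients who started stimulation, with sham alongside descriptively, and report it with an exact 95% CI.
- **Definition.** Reconcile I-c, D.1 and E.3.3 on the symptom condition. If I-c governs, count as tolerating only patients who meet both parts, and name the form items and grade that are major. The grade is the team's choice. The form has pain and skin items but none called discomfort, so say which items stand for it.
- **Criterion.** State one, with its null and the critical count for each possible active N. One option is a 90% point threshold: 17/18, 19/21, 22/24, 25/27, 27/30, 30/33 or 33/36. This is a choice, and more lenient: a true 85% rate passes 22% (18 active) or 19% (36 active) of the time. The other is a named test. If it rejects 90% or less, acknowledge that it cannot be met with 18 to 33 active patients (33/33 gives p = 0.031) and needs 36/36 at maximum size (35/36 gives p = 0.113).
- **Denominator within patient.** Measure the 75% against the stimulation the protocol called for in that patient. Cycles shortened or not given under the protocol for reasons other than adverse effects then leave that patient's stimulus period. Recompute the critical count on the evaluable active patients.

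**Cost.** Mainly wording in E.3.3, with matching text in D.1 and I-c. The form already records severity and whether an effect shortened stimulation. It has no relatedness field, and E.1 describes causality assessment only for serious adverse events. So either count listed items at the stated grade whatever their cause, which is stricter, or add the field. The denominator falls from 24–48 to 18–36 and intervals widen: 16/18 gives 65.3–98.6% against 73.0–99.0% for 22/24.

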Device use will be performed by physician investigators, technologists, and research staff who have completed training and certification in safe tDCS use. Training will include instructions on different components of the device, installing and assembling the components, charging the device prior to the first use, recharging the device after each procedure, verifying the device is charged prior to each procedure, recognizing and addressing the different Warning/Error indications (e.g., battery light flashing blue, indicating that the battery is low but can still perform at least one procedure, battery light steady red, indicating battery low error – not enough battery power to run a complete procedure, etc.) and specific instructions for returning the device to the sponsor in the event of an error notification that cannot be addressed by the site personnel, or a failure of the device to charge after three hours. All device training will be documented in a training log that will be maintained in the site regulatory binder.

D3. Subjects

Twenty four to 48 acute ischemic stroke patients who are undergoing endovascular therapy and meet study inclusion/exclusion criteria will be enrolled from Ronald Reagan Medical Center (RRMC) Emergency Department or RRMC inpatients. At last two dose tiers, patients arriving in Mobile Stroke Unit (MSU) with large vessel occlusion who are candidates for EVT will also be included for bridging stimulation en route to RRMC.

Based upon acute stroke patient referral rates to UCLA over the past 3 years, we anticipate 24 *enrollments per year*. Therefore, we estimate that the study enrollment will take 2 years to complete. Enrolled subjects will be randomized to active versus sham stimulation in 3:1 ratio.

D.3.1 Entry Criteria

Inclusion criteria

- 1) New focal neurologic deficit consistent with AIS
- 2) Age \geq 18
- 3) NIHSS \geq 4
- 4) ICA or M1 or M2 MCA occlusion on pre-thrombectomy MRA or CTA
- 5) Onset (last-seen-well) time to randomization time within 24 hours
- 6) Pre-stroke modified Rankin Scale \leq 3
- 8) Patient ineligible for IV tPA, per national AHA/ASA Guidelines
- 9) Having undergone endovascular thrombectomy with less than a complete reperfusion (<TICI 2c, 3) for receiving post-thrombectomy adjunct C-tDCS
- 10) Undergoing endovascular thrombectomy, per national AHA/ASA Guidelines for patients who are assigned to pre-thrombectomy bridging session at Tiers 5, 6

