The study sample size derives from the use of the 3+3, rule-based, modified Fibonacci, dose escalation design, with 3:1 randomization to active treatment vs sham control. There will be 6 dose tiers, reflecting increasing intensity and duration of stimulation (Figure 7). The 3+3 study design (3 patients and 1 sham) with 6 dose tiers yields a sample size of at least 24 and potentially up to 48. The 3+3 design is the classical approach to dose escalation in first-in-human studies.^{47,48} While newer, adaptive designs for dose escalation trials have been developed, they are more complex and have limited advantages when major toxicities are not expected.⁴⁹ Therefore, the rule-based, 3+3 design remains the dominantly employed approach in current dose-escalation studies. We will take every step to avoid missing data by scheduling of the follow-up visits early in visit time windows and readiness to travel to the patient's location to perform needed assessments. Should any missing data occur, primary analyses will be performed using multiple imputation, with sensitivity analyses including complete case and worst possible outcome analyses.⁵⁰

E.2.2. Baseline characteristics

The demographic and baseline clinical characteristics of the study population will be delineated with standard descriptive statistics. Categorical variables describing the clinical history, examination findings, and initial treatment will be summarized by frequencies. Continuous variables such as vital signs, laboratory results, and time variables will be characterized by means, standard deviations, and 95% confidence intervals (CI). Ordinal and non-normally distributed variables (such as the NIHSS) will be characterized by medians and interquartile ranges. Baseline characteristics will be compared between the tDCS stimulation group with sham group to assess covariate balance. Wilcoxon Rank-Sum tests will be used for continuous or ordinal variables; Fisher's exact tests and chi-square tests will be used for grouped or nominal categorical variables.

E.2.3. Safety and Tolerability (Specific Aim 1)

E.2.3.1 Dose Escalation

The study Data and Safety Monitoring Board (DSMB) will meet at the completion of each dose tier, review all safety data, and determine whether the study will proceed to the next dose tier. DSMB deliberations will be

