guided by: 1) a formal stopping/escalation rule, based on the occurrence of the lead safety endpoint, symptomatic intracranial hemorrhage (SICH), and 2) The DSMB members' clinical judgement upon review of all other safety outcomes. The formal dose escalation rule uses SICH frequency to gate the occurrence and pace of escalation through the 6 dose tiers. If no SICH occurs in the 3 active patients at a dose tier, enrollment may escalate to the next dose tier. If one SICH occurs, 3 more active (and 1 more control) patient will be enrolled at that dose tier before escalation. If 2 SICHs occur at a dose tier, further study enrollment is held until detailed review by the DSMB (Fig 6). In addition, whenever the formal SICH criteria for dose escalation has been met, the DSMB will formally meet, review the SICH data and all other safety data, and advice regarding proceeding to the next tier, continuing at the current tier, or placing the study on hold.

E.2.3.2. Primary Safety Endpoint Analysis

For the final statistical analysis of the primary SICH safety endpoint, a chi-square test will be used to detect differences in the rate of SICH between the active treatment and sham patients and higher and lower dose tiers. The treatment will be considered to have exhibited adequate safety in the current trial to proceed to future, larger, pivotal efficacy trials if tDCS results in lower or equivalent rates of SICH compared to sham.

E.2.3.3. Secondary Safety Endpoints Analysis

In secondary safety endpoint analyses, the following will be compared between the active treatment and sham patients, and between higher and lower dose tiers, using chi-squared tests: **1)** Asymptomatic ICH by 24h (intracranial hemorrhage not associated with NIHSS worsening ≥ 4); **2)** Early neurologic deterioration (worsening ≥ 4 on NIHSS during the 24-hour period after stimulation, with or without intracranial hemorrhage); **3)** All-cause mortality at day 90 (mRS); and **4)** All serious adverse events.

E.3.3. Tolerability Endpoint Analysis

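### E.3.3 attaches a one-sided 0.025 to the 90% tolerability bar without naming null or test, so the rule can require 22/24, 18/24, or a result that cannot occur at the minimum size; sham patients also count towards it.

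*Combined protocol and SAP*

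**What the plan says.** E.3.3 (Tolerability Endpoint Analysis) describes the lead endpoint as completing the protocol-assigned stimulation "without early cessation due to cutaneous, neurologic, nociceptive or other adverse effects". It then sets a working definition: "a patient will be considered to have tolerated the procedure if at least 75% of the stimulus period was completed". The treatment is generally tolerable if, "among all enrolled patients, tolerated procedures are achieved in" at least 90% "of patients, assessed with a one-sided p value of 0.025".

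No null, direction, test statistic or required count is given. Hypothesis I-c (Specific Aims) repeats the 90% figure for tolerating C-tDCS, without a p value. The chi-square, Fisher and Wilcoxon tests named elsewhere in E.2 are group comparisons and do not supply a one-sample test.

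On size, E.2.1 says the design "yields a sample size of at least 24 and potentially up to 48". Under E.2.3.1 a tier grows as follows: "If one SICH occurs, 3 more active (and 1 more control) patient will be enrolled at that dose tier before escalation". After two SICHs at a tier, "further study enrollment is held until detailed review by the DSMB". D.4 (Dose Tiers and Randomization) states that sham patients wear the cap and electrodes with no current delivered.

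**The concern.** A success rule with a stated error level should lead two analysts to the same decision from the same data. This one does not. Depending on the null, the same 24-patient result can pass, fail, or be judged against a standard that no result can reach, and the choice stays open until the data are seen. A trial ending at 24, 28 or 32 patients might have to report its lead tolerability criterion as not met despite perfect tolerance. Alternatively, it might report the criterion as met at a 75% observed rate.

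A second problem lies in the same sentence. The claim is about tolerating the current, but a quarter of the denominator receives none.

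**Working it through.** **Inputs.** Benchmark 0.90, one-sided 0.025, all enrolled patients (E.3.3). Six tiers, 3 active + 1 sham each, expandable by 3 + 1 (E.2.1, E.2.3.1).

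**The plan's own figure.** 6 × (3 + 1) = 24 and 6 × (6 + 2) = 48, so the 24 to 48 range reproduces. Planned totals rise in steps of 4. The plan gives no power or required count for tolerability.

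**Reading 1: test that the rate exceeds 90%.** For a perfect result n/n, exact p = 0.9^n, mid-p = half of that, and score z = (1 − 0.9)/√(0.09/n).

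**Reading 2: test for shortfall below 90%.** Lower-tail p = P(X ≤ k | n, 0.90). The sixth column gives this p at the smallest count that meets the observed bar. The last column gives the smallest count that is not significantly below 90%.

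| N | exact p, n/n | score p, n/n | mid-p, n/n | observed 90% bar | lower-tail p at bar | not significantly below 90% from |
|---|---|---|---|---|---|---|
| 24 | 0.0798 | 0.0512 | 0.0399 | 22 | 0.708 | 18 (75.0%) |
| 28 | 0.0523 | 0.0389 | 0.0262 | 26 | 0.785 | 22 (78.6%) |
| 32 | 0.0343 | 0.0297 | 0.0172 | 29 | 0.633 | 25 (78.1%) |
| 36 | 0.0225 | 0.0228 | 0.0113 | 33 | 0.712 | 29 (80.6%) |
| 40 | 0.0148 | 0.0175 | 0.0074 | 36 | 0.577 | 32 (80.0%) |
| 44 | 0.0097 | 0.0135 | 0.0048 | 40 | 0.653 | 35 (79.5%) |
| 48 | 0.0064 | 0.0105 | 0.0032 | 44 | 0.720 | 39 (81.3%) |

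*Reading 1 results.* No count passes at 24 by any of the three methods. By the exact and score tests, 28 and 32 cannot pass either, and the first planned size that can is 36. From 36 to 48 the exact test allows no failure; 47/48 gives p = 0.040. Exact power is then the chance of zero failures. At assumed true rates of 95%, 98% and 99% it is 16%, 48% and 70% at N = 36 (0.95^36 and so on), and 8.5%, 38% and 62% at N = 48.

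*Reading 2, bar kept.* Every result that meets the bar has a lower-tail p far above 0.025 (smallest 0.577, at N = 40), so the p value never alters the decision.

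*Reading 2, test replaces the bar.* At N = 24 the test rejects only at 17 or fewer (p = 0.0075; 18/24 gives 0.028). A true rate of 75% would pass 61% of the time. At N = 48, 39/48 passes.

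**Sham dilution.** The minimum size has 18 active and 6 sham patients. If all 6 sham patients tolerate the procedure, 22/24 = 91.7% overall corresponds to 16/18 = 88.9% active. The two rates lie on opposite sides of the bar.

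**Stimulus period, Tiers 5 and 6.** Three 20-minute cycles make 60 minutes, and 75% is 45. Under D.1 and D.4 the first cycle may be cut short so as not to delay EVT, and the later two follow only incomplete reperfusion. If the period means the full 60 minutes, a patient who reaches TICI 2c or 3 receives at most 20. A patient with both later cycles complete (40 minutes) needs at least 5 minutes of the first. Either could count as intolerant with no adverse effect.

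**The case against.** **Some methods pass 24/24.** A signed-root likelihood-ratio test gives p = 0.012 and a Jeffreys lower limit is 0.9016. But 24/24 has probability 0.080 at a true 90%, so any non-randomised rule that accepts it has a one-sided error of at least 0.080. Mid-p accepts 32/32 (0.017) and 47/48 (0.023), so the statements about 28 to 48 depend on the method; failure at 24 does not, for a test that truly holds 0.025.

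**The trial may be larger.** D3 expects 24 enrollments a year and says "we estimate that the study enrollment will take 2 years to complete", which points to 48. This stands: a reader might infer that the criterion is unattainable throughout, and the documents do not support that, since 48/48 passes. But under the formal rule the total exceeds 24 only after a SICH. It can also end below 24 if enrollment is held and not resumed.

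**The 0.025 may be harmless decoration.** A reader might infer that a shortfall check has no effect. That is true only if the observed bar remains a separate hurdle. E.3.3 says the 90% criterion is assessed with the p value, so the test may itself be the rule, and the criterion then loosens to 18/24.

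**Tiers 5 and 6.** A reader might infer that shortened or skipped cycles will be scored as intolerance. The text does not establish this. The lead endpoint refers to protocol-assigned stimulation, the 75% rule is introduced as following from it, and the tolerability form records whether an adverse event shortened stimulation. What survives is an undefined term.

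**Limited weight.** Tolerability is not primary and does not gate escalation, and D.6.10.2 rests further development on all outcome measures. This stands.

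**Conclusion.** The concern holds in this form. The tolerability rule is underspecified, and its readings give materially different requirements at the minimum size: 22/24, 18/24, or nothing attainable. As a true level-0.025 test against 90% it cannot be met at 24. By the exact test it needs at least 36 patients with no failures. Counting sham patients can move the observed rate across the bar.

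The results for 24 need only the plan's own benchmark and error level. The power figures and the 75% pass probability rest on assumed true rates, because the documents give none. The Tier 5 and 6 issue is a clarification, conditional on reading the period as 60 minutes. The point should be fixed before data are seen, but it does not threaten the primary safety assessment.

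**What to change.** **Recommended.** Delete the 0.025 test against 90%. Declare tolerability on an observed rate of at least 90% among active patients, which matches the population of Hypothesis I-c. At the minimum size that is 17/18, with exact (Clopper-Pearson) 95% interval 72.7% to 99.9%. Also report all enrolled patients (22/24: 73.0% to 99.0%).

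**If a test is kept.** Prespecify a lower unacceptable rate that the sponsor justifies, the exact test, and the required count for each possible N, with the observed 90% bar alongside. The bar matters: against an assumed null of 70%, used only as an illustration, 34/40 (85%) would be significant (p = 0.024) while missing the protocol's own 90%.

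**Clarification.** Define the stimulus period as the stimulation assigned to that patient. Reconcile the 75% rule with the shortened first cycle and conditional later cycles in Tiers 5 and 6, so that time not delivered for reasons other than adverse effects is not scored as intolerance. D.6.4 already records when C-tDCS was aborted before EVT.

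**Cost.** Wording only, no extra patients. The denominator falls from 24 to 18 at the minimum size and the interval widens. An observed bar is also a weak filter: 17/18 or better occurs with probability 10% if the true rate is 80%, 22% at 85%, and 77% at 95%. The most lenient planned size is 21 active patients (19/21), where the first two figures are 18% and 37%. Keeping a test means that the claim is made against the lower null, not against 90%.
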